7.6.4 Analysis of Primary and Secondary Immunogenicity Endpoints

7.6.4.1 Analysis of Immunogenicity Endpoint (GMT/GMC and GMR) (Estimand 2)

The primary immunogenicity analyses will be performed using the mITT set evaluating responses measured by neutralizing antibody assay. Secondary immunogenicity analyses will be performed using the mat set evaluating responses measured by binding antibody assays.

Total NAbs and BAbs titers will be summarized using descriptive statistics (number of subjects (n), median, minimum and maximum) by each time point: Baseline, Days 14, 28, 42, 56, 208, 236, Early Termination. Geometric mean titers (GMT) with corresponding 95% CIs will be provided. The 95% CIs will be calculated based on the t-distribution of the log-transformed values then back transformed to the original scale for presentation. GMTs and corresponding 95% CIs will be plotted at each timepoint. GMFRs with corresponding 95% CIs will be provided at each post-baseline timepoint over baseline. The 95% CIs will be calculated based on the t-distribution of the log-transformed values then back transformed to the original scale for presentation. GMFRs and corresponding 95% CIs will also be plotted at each timepoint. Analyses will be repeated by subgroups as follows: gender, age group

Arcturus Therapeutics, Inc.
Protocol ARCT-021-04, Version 6.0

ARCT-021
09 March 2022

(≥ 18 to < 56 and ≥ 56 years) and country. Scatter plots of NAbs and BAbs titers at specific time points will be presented.

For the priming vaccination period an analysis of covariance model (ANCOVA) will be fitted to the natural log transformed neutralizing antibody titers measured against SARS CoV 2 with terms for treatment group, age group (≥ 18 to < 56 and ≥ 56 years) (stratification factor at randomization) and natural log baseline titer by each post-vaccination immunogenicity visit. The geometric least squares mean (GLSM) and corresponding 2-sided 95% CI for each treatment group will be provided by visit. Geometric mean ratio (GMR), estimated by the ratio of GLSM, and the corresponding 95% CI will be provided to assess the difference between ARCT-021 vs. placebo groups at each visit. No adjustments for multiplicity will be carried out. ANCOVA analyses will be repeated by the following subgroups: gender and country.

The above summaries and analyses will be present for binding antibody concentrations as well.

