4.4.12. Booster Modified Intent-to-Treat Analysis Set

The Booster Modified Intent-to-Treat (Booster mITT) analysis set includes all mITT participants who has at least one immunogenicity data evaluable by the assay in use with valid results during the booster vaccination period. Participants will be analyzed according to the vaccine assigned. If a participant was not randomized to a booster dose on the Day 208 visit but has immunogenicity data collected during the booster vaccination period, the participant will be summarized with the placebo booster group.

- Note: The Booster mITT analysis set for re-enrolled participants consists of all re-enrolled participants who has at least one immunogenicity data evaluable by the assay in use with valid results during the booster vaccination period while as a re-enrolled participant. Immunogenicity data for re-enrolled participants will only be listed (i.e., will not be included in the summary tables).

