8.2.2. Supportive Analyses of Primary and Secondary Immunogenicity Endpoints

8.2.2.1. Supportive Analyses of Estimand 2

To assess the magnitudes of the differences between the treatment groups (ARCT-021 vs. Placebo) in SARS-CoV-2 neutralizing antibody (NAbs) and SARS-CoV-2 binding antibody (BAbs) endpoints, an analysis of covariance (ANCOVA) model will be fitted to the natural log transformed neutralizing antibody titers measured against SARS CoV 2 with terms for treatment group, age group (≥ 18 to < 56 and ≥ 56 years) (stratification factor at randomization) and natural log baseline titer by each post-vaccination immunogenicity visit. No imputation of missing data will be done.

The geometric least squares mean (GLSM) and corresponding 2-sided 95% CI for the antibody titers for each treatment group will be provided by visit. The GLSM and corresponding 95% CI results in log-transformed scale estimated from the model will be back-transformed to obtain these estimates in the original scale. Geometric mean ratio (GMR), estimated by the ratio of GLSM and the corresponding 2-sided 95% CI will be provided to assess the treatment difference between ARCT-021 group vs. placebo group at each visit.

ANCOVA analyses will be performed for the priming vaccination period on mITT analysis set only.

8.2.2.2. Supportive Analyses of Estimand 3

The common difference of seropositivity and seroconversion rates and 95% CIs between each vaccine dose group and the placebo will be estimated using the Miettinen-Nurminen method with age group (≥ 18 to < 56 and ≥ 56 years) as stratification factor for each time point.

Miettinen-Nurminen analyses will be performed for the priming vaccination period on mITT analysis set only.

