8.3. Exploratory Immunogenicity Analyses

8.3.1. Assays for Response to SARS-CoV-2 Variants

To address the exploratory immunogenicity objective to evaluate responses to SARS-CoV-2 variants, the binding antibody responses of ARCT-021/ARCT-154/ARCT-165 will be compared to placebo for the booster vaccination period. SARS-CoV-2 binding antibodies (BAbs) will be tested using an MSD multiplex assay which measures total immunoglobulin G (IgG) against the full-length spike, RBD and N antigens of the beta strain. Neutralizing antibodies against the beta strain of SARS-CoV-2 will also be measured:

- IgG measured against the Nucleocapsid (N) antigen of the beta variant (B1.351) of SARS-CoV-2 (VAC83_ECL_CoV-2_N)
- IgG measured against the RBD antigen of the beta variant (B1.351) of SARS-CoV-2 (VAC83_ECL_CoV-2_RBD)

- IgG measured against the Spike antigen of the beta variant (B.1.351) of SARS-CoV-2 (VAC83_ECL-CoV-2_S_B.1.351)
- Microneutralization antibody concentration against the beta variant (B.1.351) of SARS-CoV-2 (VAC85_MN_CoV-2)

Similar estimands will be used as for the secondary objective.

The LLOQ for each assay is shown below:

- VAC83_ECL_CoV-2_N (AU/mL; 1:500 dilution): 27
- VAC83_ECL_CoV-2_RBD (AU/mL; 1:500 dilution): 19
- VAC83_ECL_CoV-2_S_B.1.351 (AU/mL; 1:500 dilution): 18
- VAC85_MN_CoV-2 (AU/mL; 1:5 dilution): 14

Assays for other variants may be analyzed as available as part of the exploratory analysis.

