9.5. Physical Examinations and Emergency Room and/or Hospitalization for COVID-19 Assessment

Listings of complete physical examinations and symptom directed physical examination will be provided. Listings of emergency room visits and/or hospitalization for COVID-19 assessment will be provided.

10. Interim analyses

Three interim analyses will be performed.

- The first interim analysis will focus on safety and will evaluate available safety data for all participants who were initially enrolled as of 05 February 2021 when they have completed Day 7 or Early Termination visit procedures.
- The second interim analysis will evaluate available safety and immunogenicity data for all participants who were initially enrolled as of 05 February 2021 and when they have completed Day 28 or Early Termination visit procedures.

- The third interim analysis will evaluate available safety and immunogenicity data for all participants after they have completed Day 56 or Early Termination visit procedures.

At each of these interim analyses, the datasets from immunogenicity assessments may not contain all participants' data. However, the data cuts outlined above are intended to inform additional clinical development considerations, including selection of ARCT-021 dose for booster administration and selection of final dose and schedule for ARCT-021 administration in the Phase 3 study. The data will be monitored prior to and the database will be locked after the third interim analysis to inform an interim clinical study report.

All available safety and immunogenicity data will be summarized. Blinded data will be shared with the SRC and unblinded data will be shared with the DSMB and sponsor.

Please note that a dry run of safety analysis TLFs will be delivered unblinded to sponsor before the final analysis (i.e., prior to final database lock).

11. Change from Planned Analysis

1. Protocol Section 2.3 states the following exploratory objective: *“To evaluate cell-mediated immune (CMI) responses in participants receiving ARCT-021, ARCT-154, and ARCT-165 versus placebo for priming vaccination”*. This exploratory objective has been revised in SAP section 2.3. to the following: *“To evaluate cell-mediated immune (CMI) responses in participants receiving ARCT 021 versus placebo for priming vaccination.”*
 - Justification: ARCT-154 and 165 are not given as priming vaccinations. This update is to clarify the intent of this exploratory analysis.

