Estimand Label	Estimand 2 (Geometric Mean Titers/Concentrations)
Estimand Description	
The GMT of NAbs (primary) and BAbs (secondary) against SARS-CoV-2 up to Early Termination after first vaccination with ARCT-021 of each group (5.0, 7.5 µg, or placebo) and with/without booster dose in healthy adults.
 
Interest will lie in comparing the GMT of each dosing regimen to placebo based on the Geometric Mean Ratio (GMR).
 
The hypothetical strategy is used to estimate antibody levels had all scheduled vaccinations been received, and without subsequent SARS-CoV-2 infection or influence from immune-modifying drugs or non-study vaccines. The principal stratum strategy excludes those with active or early SARS-CoV-2 infection within 7 days after the first study vaccine administration.

Analysis Population	Vaccinated healthy adults (as defined by eligibility criteria) without active or early SARS-CoV-2 infection (infection within 7 days after the first vaccination).
Endpoint	Total NAbs (primary) and BAbs (secondary) specific for the SARS-CoV-2 measured pre- and post-priming vaccine administration (on Day 0, 14, 28, 42, 56, and 208) and following booster vaccine administration (Day 236, Early Termination).
Treatment Conditions	Placebo or 5.0 µg or 7.5 µg ARCT-021 administered on Day 0, Day 28; placebo, ARCT-021, ARCT-154, or ARCT-165 administered on Day 208.
Population-Level Summary	The GMT and GMR of comparisons of interest at each time point. GMR will compare responses in placebo-, ARCT-021-, ARCT-154-, and ARCT-165-vaccinated groups at relevant timepoints. For additional considerations on population-level summary see the SAP.
Intercurrent Event Strategy	
IcEv1 (Death)	Hypothetical strategy
IcEv2 (Missed dose)	Hypothetical strategy
IcEv3 (Immune-modifying)	Hypothetical strategy
IcEv4 (Early infection)	Principal stratum strategy (based on study phase)
IcEv5 (Study infection)	Hypothetical strategy
Rationale for Strategies	Hypothetical strategy is used to understand antibody levels achieved through receiving scheduled vaccination, without subsequent SARS-CoV-2 infection and without any influence from immune-modifying drugs or non-study vaccines. In estimation, the hypothetical uses a statistical model on the mITT (excluding data points following intercurrent events and not complete removal of all data for the participant).

Estimand Label	Estimand 3 (Rise/Seroconversion)

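### Estimand 2 promises a geometric mean ratio across the booster groups, but the only model that yields a ratio is confined to the priming period

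*SAP*

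**What the plan says.** Estimand 2 covers neutralizing and binding antibody levels, and its endpoint includes Day 236 and Early Termination after the booster. Its population-level summary states that "GMR will compare responses in placebo-, ARCT-021-, ARCT-154-, and ARCT-165-vaccinated groups at relevant timepoints" (SAP Table 13-5; the same sentence is in Protocol Table 7-2). SAP 8.3.1 adds that beta-strain binding responses to the three boosters "will be compared to placebo for the booster vaccination period". SAP Section 11 confirms that "ARCT-154 and 165 are not given as priming vaccinations".

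On estimation, SAP 8.2.2.1 says: "Geometric mean ratio (GMR), estimated by the ratio of GLSM and the corresponding 2-sided 95% CI will be provided", for ARCT-021 against placebo. It then sets the scope: "ANCOVA analyses will be performed for the priming vaccination period on mITT analysis set only". Protocol 7.6.4.1 has the same scope: "For the priming vaccination period an analysis of covariance model (ANCOVA) will be fitted". The between-group rate differences for Estimand 3 are limited in the same way: "Miettinen-Nurminen analyses will be performed for the priming vaccination period on mITT analysis set only".

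On the comparator, SAP Table 4-1 defines one ARCT-primed control column, H1, for placebo booster and no booster together. SAP 4.4.12 says of anyone not randomized to a booster who has booster-period immunogenicity data that "the participant will be summarized with the placebo booster group".

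**The concern.** Followed as written, the plan cannot deliver the ratio it names. A reader who wants to know how ARCT-154 or ARCT-165 performed against placebo as a booster would have to set separate group intervals side by side. In the Booster mITT tables that means using a control column that is partly non-randomized. People who are not boosted are not a random subset: Protocol 4.2.2 stops further dosing for, among other reasons, Grade 3 solicited events, related severe events and off-study COVID-19 vaccine.

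The 1:1:1:1 booster randomization in Study Groups 1 to 3 is the study's only placebo-controlled randomized evidence on ARCT-154 and ARCT-165, and the Protocol synopsis says these data will inform development planning. If the conflict stays in the plan, the comparator, covariates and model for any booster ratio would be chosen after the data are seen.

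**Working it through.** **Tracing the ratio through the plan**

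- *Promise:* a GMR including ARCT-154 and ARCT-165 groups. Both are booster-only, so this is a booster-period GMR.
- *Estimator:* the ratio of ANCOVA geometric least squares means (SAP 8.2.2.1, Table 13-6; Protocol 7.6.4.1, Table 7-4), priming period only.
- *Output list (SAP 8.4):* the ANCOVA and Miettinen-Nurminen rows are marked for the priming period only. The booster rows for neutralizing and binding antibody contain only the GMT/GMFR/seroconversion/seropositivity summary. The beta-strain assays of SAP 8.3.1 have no row.
- *Recorded changes (SAP Section 11):* four items, none of which drops the booster GMR.
- *Further detail:* Table 13-5 sends the reader to the SAP, which is the same document.

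**Whether planned outputs fill the gap**

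- Booster GMFR does not. SAP 4.1 sets baseline before the first priming dose for both phases, so booster-period fold rise combines priming and booster effects.
- Booster mITT gives group GMTs with the mixed H1 control.
- Booster PP requires receipt of the correct doses including the booster (SAP 4.4.13), so unboosted people are excluded, but no ratio is produced.

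**The plan's own figures**

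The SD of 1.2 on the log scale matches the stated CoV of 180%: √(exp(1.2²) − 1) = 1.795. The plan's only power figure for a titre comparison is above 99% for a 2-fold difference at 75:75. With ln 2 = 0.693 and SE = 1.2 × √(2/75) = 0.196, the normal approximation gives Φ(3.537 − 1.960) = 94.3%; 150:150 gives 99.9%. That mismatch is a separate matter, and nothing below depends on it. The plan gives no precision figure for a booster ratio.

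**Precision a booster GMR would have**

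Inputs:
- SD 1.2 (SAP 4.2), a priming-period assumption taken to carry over.
- 112 per arm: 600 × 3/4 = 450 ARCT-primed, and 450/4 = 112.5, with no attrition.
- 25 per group: the stated minimum in SAP 4.2.
- 50: an assumed intermediate case.
- Correlations ρ of 0.5 and 0.7 between Day 208 and Day 236 log titre: assumed, with no source in the documents.

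The 95% limits are the GMR divided and multiplied by exp(1.96 × 1.2 × √(2/n) × √(1 − ρ²)).

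| n per arm | unadjusted | ρ = 0.5 | ρ = 0.7 |
|---|---|---|---|
| 112 | 1.37 | 1.31 | 1.25 |
| 50 | 1.60 | 1.50 | 1.40 |
| 25 | 1.95 (1.98 with the t quantile) | 1.78 | 1.61 |

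**Cost of reading separate intervals instead**

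Two group-level 95% CIs separate only when the ratio exceeds exp(2 × 1.96 × 1.2/√n). That is about 1.56 at n = 112 and 1.95 at n = 50, whereas the unadjusted CI for the GMR excludes 1 at 1.37 and 1.60.

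**The case against.** The best case for the plan is that descriptive booster reporting was intended. Booster immunogenicity is exploratory, Protocol 7.6.5 says exploratory endpoints are analyzed descriptively, and Protocol 7.2 disclaims hypothesis testing. The booster endpoint list in SAP Table 2-3 contains no GMT or GMC ratio, although the priming lists do. Even for priming, the ANCOVA is labelled supportive, and the main estimation of Estimand 2 is group GMT and GMFR with CIs, which the booster period does receive. The study was terminated early, and SAP Section 1 warns of limited interpretation beyond Day 56.

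This lowers the weight of the point but does not remove it. A ratio with a CI is estimation, so it fits a descriptive study without tests. An intention to omit it would show in the estimand sentence, in SAP 8.3.1 or in Section 11, and it shows in none of them.

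Two stronger readings are tempting and should be resisted. A reader might infer that booster responses are not estimated at all. They are: group GMT, GMFR, seroconversion and seropositivity with 95% CIs are planned, and only the ratio is missing. A reader might also infer that every booster table uses a contaminated control. The Booster PP tables do not, because unboosted people cannot enter that set. Nor are Groups 1 to 3 the only randomized booster comparison: Study Group 4 participants who did not re-enroll are randomized 1:1:1 among the active boosters, without placebo.

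**Conclusion.** The point holds as an inconsistency between a stated estimand and its planned analysis. The booster-period GMR named in Estimand 2, and the comparison with placebo named in SAP 8.3.1, have no estimator, no output and no recorded withdrawal. The mixing of randomized placebo with unboosted participants is confined to the Booster mITT tables; its extent cannot be judged from the documents. The primary objective is unaffected, since ARCT-021 against placebo in the priming period has its GMR and CI.

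What is forgone is a direct ratio with an unadjusted 95% CI factor between 1.37 (a ceiling, since it assumes no attrition) and about 1.95 to 1.98 (the stated minimum of 25). At that minimum an observed 2-fold ratio would have limits of about 1.01 and 3.96 (2 divided and multiplied by 1.98). These figures rest on SD 1.2 carrying over from priming; the gains from adjustment rest on assumed correlations. The change should be made, as an exploratory matter.

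**What to change.** Add to SAP 8.2.2.1 an exploratory ANCOVA of log titre at Day 236:

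- *Population:* originally enrolled, ARCT-primed participants (Study Groups 1 to 3) randomized 1:1:1:1 to booster. Re-enrolled participants stay out, since SAP 4.4.12 only lists their immunogenicity data.
- *Terms:* booster arm, priming group, age group and log Day 208 pre-booster titre. State that this covariate is an exception to the SAP 4.1 baseline definition.
- *Report:* the GMR with 95% CI of each booster against randomized placebo, leaving participants not randomized to a booster out of the reference.
- *Assays:* neutralizing and binding antibody, Wuhan and beta strains, with matching rows in SAP 8.4.

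If the sponsor does not want this analysis, remove the booster groups from the Estimand 2 GMR sentence, reword SAP 8.3.1, and record the change in SAP Section 11.

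The cost is one further model on data already collected. It gives three ratios per assay: with four Wuhan and four beta assays, 3 × 8 = 24 exploratory ratios, with no multiplicity claim. The alternative costs only text, but leaves the placebo-controlled booster randomization without a planned contrast.
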